## Abbreviations

BAD: Bile Acid Diarrhoea, BSF: Bristol Stool Form scale, C4: 7 $\alpha$ -hydroxy-4-cholesten-3-one, CDCA: chenodeoxycholic acid, DMA: Danish Medicines Agency, ELISA: enzyme-linked immunosorbent assay, FGF19: fibroblast growth factor 19, GSRs: Gastrointestinal Symptoms Rating Scale, HPLC: high performance liquid chromatography, HRQoL: Health Related Quality of Life, IBS-D: Diarrhoea-predominant irritable bowel syndrome, LC-MS/MS: liquid chromatography-tandem mass spectrometry, ROC: Receiver Operating Characteristics, SeHCAT: Selenium conjugated Tauro-homocholelic acid retention test, SF36v2: Short Form 26 version 2, SHS: Short health Scale.

## Aims

1. To determine the efficacy and safety of colestevlam for treating bile acid diarrhoea (BAD).
2. To correlate both the current scintigraphic Selenium conjugated Tauro-homocholic acid retention test (SeHCAT) and the biochemical marker of BAD 7 $\alpha$ -hydroxy-4-cholesten-3-one (C4) with colestevlam treatment response, and to validate the cut-off values determined in the VABAD trial (1).

## Summary of expected improvements from the study

The present diagnosis of BAD rests on the radionucleotide based SeHCAT test that has limited accessibility. Patients with BAD therefore often endure an extensive diagnostic workup including endoscopies before referral for SeHCAT. Consequently, the patients are often misdiagnosed and suffer impaired quality of life although treatment for BAD exists. A biochemical test will allow timely screening of patients with chronic diarrhoea in analogy with tests for celiac disease, increase awareness of BAD, reduce diagnostic delay, and the exposure to unnecessary invasive examinations. Demonstrating the treatment effect of colestevlam in a randomised placebo-controlled trial and correlating each biochemical test result with the subsequent treatment effect will improve both the diagnostic strategy and the treatment of BAD considerably. This crucial link between test and expected treatment effect is currently missing and providing this will help doctors treat and advise their patients better.

## Background

### Bile acid diarrhoea

Bile acid diarrhoea (BAD) is a common cause of chronic watery diarrhoea affecting an estimated 1% of the general population (2). BAD is detected in 20–30% of patients with diarrhoea predominant irritable bowel syndrome (IBS-D) (3), up to 40% of patients with microscopic colitis (4), and in patients with Crohn's disease without inflammatory activity (3, 5-9).

Bile acids are synthesised in the liver, excreted in the bile and facilitate the lipid absorption in the small intestine as micelles. Bile acids that are not thus absorbed are normally reabsorbed in the terminal ileum by the ileal bile acid transporter and returned to the liver via the portal vein. The bile acid pool recirculates approximately 20 times per day and 95–97% is reabsorbed at each passage of the small intestine (5, 7). Non-absorbed bile acids enter the large bowel and give active secretion when present in higher concentrations causing watery diarrhoea.

Bile acid diarrhoea is historically classified as:

- Type 1 secondary to disease in the terminal ileum and resection of the terminal ileum.

Type 2 idiopathic or primary BAD

Type 3 secondary to other diseases such as microscopic colitis and cholecystectomy.

New insight into the regulation of bile acid synthesis and its enterohepatic circulation has demonstrated that patients with primary BAD have normal reuptake of bile acids, and overproduction of new bile acids that surpass the ileal re-uptake capacity (5, 7, 8, 10). This has provided new possibilities for both diagnosis and treatment of BAD.

### **Present diagnosis of bile acid diarrhoea**

The present diagnostic test for BAD is the SeHCAT retention test that originally was introduced by Thaysen (11). The Selenium decays by  $\gamma$ -emission with a half-life of 120 days and when bound to Taurine-conjugated homocholic acid (HCA) it recirculates in the enterohepatic circulation. The ratio between  $\gamma$ -emission measured seven days apart is the test result and reflects the loss to the large intestine. Retention values representing severe (SeHCAT retention 0–5%), moderate (5–10%) and mild BAD (10–15%) have never been validated in placebo-controlled trials (12), but usually moderate and severely reduced retention is associated with diarrhoea and with treatment effect (12). The SeHCAT test is not available in the US and many other countries and Selenium is manufactured in one facility only. Thus, diagnosis of BAD is often delayed and misdiagnosis is common as reflected by the high proportion of BAD among IBS-D patients (3). In lack of better options, clinicians may rely on the subjective treatment effect of a bile acid sequestrant reported by the patient. This approach has not been validated (13) and has several diagnostic pitfalls making the interpretation difficult (13, 14). Bile acids can be measured in the stools but it is cumbersome and used only for research purposes (15).

## Biochemical tests in our population – choice of C4 cutoff

We studied FGF19 after stimulation with a mixed meal (30) and then with combinations of the meal plus chenodeoxycholic acid (31) and pilot results were promising. Based on these preliminary results, we did a prospective validation study (VABAD) of 71 consecutive diarrhoea patients referred for SeHCAT. We found that neither stimulated nor fasting FGF19 were better than C4. The fasting FGF19 receiver operating characteristics (ROC) analysis versus SeHCAT ≤ 10% showed an area under the curve (AUC) of 0.73 and for C4 it was 0.83. Thus, C4 is the better biochemical test. Of the 71 VABAD patients, 59 fulfilled the Hjortswang criteria for diarrhoea (described below) that is a prerequisite in SINBAD. Table 1 shows ROC results for this subpopulation. The C4 cut-off value of 46 ng/mL had optimal combined diagnostic characteristics with a diagnostic accuracy of 74%. 13 (22%) of the 59 patients had C4 > 46 ng/mL. The cut-off > 58 had higher PPV, and 11 of 59 (19%) had C4 > 58ng/mL. We chose the 46 ng/mL cutoff for the primary endpoint to keep false negative test results at a minimum.

TABLE 1 Results from the VABAD study	SeHCAT≤10% N=25 Median (IQR)	SeHCAT>10% N=34 Median (IQR)	ROC analysis, AUC (95% CI)	Cutoff for positive test	Sens./spec. (%)	PPV/NPV (%)
Fasting C4	47 (21–71)**	11 (9–23)	0.82 (0.71–0.93)**	C4 > 25	72 / 82	64 / 80
				C4 > 46	52 / 91	72 / 74
				C4 > 58	44 / 94	77 / 70
Fasting FGF19	75 (57–146)*	115 (8–220)	0.69 (0.54–0.83)*	FGF19 ≤ 85	60 / 77	65 / 72
FGF19 in pg/mL and C4 in ng/mL. The statistical significance of the ROC curves was tested nonparametric versus true area=0.50. *p=.02; **p=.00003						

## Plasma bile acid species

In the VABAD study, patients with bile acid diarrhoea had fewer secondary bile acids in plasma, less lithocolic acid and less sulfate-conjugated bile acid species (1). The diagnostic utility of these possible biomarkers is yet unclear. However, the VABAD study was not powered to make conclusions in this subject. Therefore, we will assess this in further exploratory analyses.

## Faecal bile acids in diagnosis of bile acid diarrhoea

Measurements of faecal bile acids are used for diagnosis of BAD in the USA (15). Excretion of total bile acids in 48-hours on a set diet has primarily been used. However, this procedure is cumbersome. Increased faecal primary bile acids > 5% and > 10% possible are alternatives (32, 33). Further, it is expected that patients with bile acid diarrhoea in adjunct to increased primary bile acids in faeces will have less secondary bile acid species. Recently, a combination of primary bile acids >10% in a random single stool sample combined with elevated C4 was shown to be a good diagnostic test (34). Further, primary bile acids correlate well with SeHCAT; levels > 15% had 83% PPV for SeHCAT <10% (35). It is plausible that a combination of C4 with elevated primary fecal bile acids could correlate better to the SeHCAT scintigraphy and to treatment response than C4 alone. However, there only are few reports, and therefore we will assess this in exploratory analyses.

## Treatment of Bile Acid Diarrhoea

Based on observational data, sequestrants such as cholestyramine, colesevelam, and colestipol seem effective treatments of BAD (12). They bind to anions like bile acids and these are then excreted with the faeces lowering cholesterol and alleviating symptoms of bile acid diarrhoea. All are licensed for treating hypercholesterolaemia, but cholestyramine has the additional indication for BAD. Cholestyramine is a well-established treatment for BAD, but there are no placebo-controlled trials with cholestyramine for BAD since formulating a placebo for cholestyramine has been impossible. One recent study compared cholestyramine with hydroxypropyl cellulose as an intended placebo in 26 participants with functional diarrhoea (36). Unfortunately, hydroxypropyl cellulose had an active effect with a per protocol (PP) response rate of 38% compared with 64% for cholestyramine ( $p=0.22$ ). A 23% dropout rate for cholestyramine reflects the side effects of cholestyramine and the intention to treat (ITT) cholestyramine response rate dropped to 58%.

Colesevelam is used off-label for treating BAD often as second-line therapy due to its higher price, however many BAD patients who do not tolerate cholestyramine benefit from colesevelam, and because of this placebo-controlled studies have been warranted (13, 37). A placebo-controlled trial of colesevelam for suspected BAD in patients with Crohn's disease and diarrhoea despite inflammatory remission (i.e. suspected BAD), found diarrhoea ITT remission rates of 67% (10/15) for colesevelam and 27% (3/11) for placebo ( $p=0.057$ ). Unfortunately, the extreme inclusion and exclusion criteria caused slow recruitment and the study was terminated prematurely (38).

A recent open, non-controlled trial with obeticholic acid, a potent FXR agonist that stimulates FGF19 synthesis, demonstrated that obeticholic acid reduced bile acid synthesis and had a clinical effect in patients with primary BAD and some cases of type 2 BAD (39). This demonstrates the effect of a new pharmacological class of treatment for BAD.

## Design

Randomised, placebo-controlled, parallel groups, double-blinded multicenter, phase IV trial.

### **Null hypothesis:**

Colesevelam and placebo have the same effect on BAD.

### **Intervention:**

Colesevelam (tablets of 625mg) or identical placebo capsules. One to three capsules taken twice daily. Start dose is two capsules twice daily. The dose is titrated by a study nurse who is independent of the investigators.

Parallel arms of 12 days blinded treatment, of which the first five days is run-in and the last seven days measure endpoints.

## Study subjects

### **Inclusion criteria**

- Patients referred to Clinical Physiological/Nuclear Medicine departments for SeHCAT at Holbæk, Hvidovre, Aarhus, and Aalborg University Hospitals
- Suspected BAD
- $\geq 18$  and  $< 80$  years of age.
- Women of fertile age must use safe contraception during the treatment part of the study
  - spiral or hormonal contraception, ie. birth control pill, hormonal implant, transdermal patch, vaginal ring, or contraceptive depot injection.
  - Sexual abstinence from heterosexual intercourse. May be accepted as safe contraception by the investigator in a case by case assessment a
  - Vasectomised partner
- Ability to give informed consent after written and oral information in the Danish language

Note a) sexual abstinence from heterosexual intercourse is deemed a highly effective method of anticonception by the Clinical Trials Facilitation Group. It is accepted in this trial only because the duration is short – three weeks.

### **Exclusion criteria**

- Inflammatory bowel disease, including microscopic colitis
- Acute suspected or proven viral gastroenteritis within the recent 4 weeks
- Acute non-viral gastroenteritis within the recent 8 weeks
- Investigator-assessed debilitating chronic disease e.g. WHO performance score 3–5

- Prior treatment with colesevelam
- Treatment with laxatives or anti-diarrhoeal drugs during the study
  - Except for stable dose the last four weeks of psyllium husk and opioids for pain
- Pregnancy
- Breastfeeding women
- Crucial medication that cannot be separated appropriately from colesevelam
  - i.e. taken one hour before or 4 hours after colesevelam
- Oral anticoagulation, both warfarin, and new oral anticoagulation
- Treatment with cyclosporine within two months
- Bowel obstruction (subileus or ileus)
- Biliary obstruction
- Short bowel syndrome
- Bowel ostomy
- Allergy to colesevelam or its constituents
- Allergy to placebo constituents (excluding lactose)
- Investigator-assessed high risk of non-compliance
- If on statin/fibrate medication, unwilling to pause medication between study visits 1 and 2

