## Endpoints

### Primary endpoint

Placebo-controlled ITT diarrhoea remission rate defined by the Hjortswang criteria for colesevelam in patients with BAD defined by  $C4 > 46$  ng/mL.

**Handling of missing data:** drop-outs are set as treatment failures in the ITT analysis if less than five of the last seven treatment days that comprise the endpoint assessment period are complete. If five or more of these days are complete, a mean of these days will be used for calculating the Hjortswang response criterium.

**Statistical analysis:** data will be longitudinally correlated (baseline, run-in, endpoint assessment period for each patient) and nested within study sites. Thus, data will not be independent and cannot correctly be assessed with simple statistical tests. Therefore, we will fit an appropriate generalized linear mixed-effects model with an unstructured covariance pattern of the chance of response with colesevelam versus placebo. In addition, baseline adjustments for the severity of

diarrhoea (mean per day sum of Bristol type 6 and 7 stools) and the severity of bile acid malabsorption (visit 2 C4 value) will be made to avoid skewed randomisation of these prognostic covariates by chance (40). This baseline adjustment is clinically relevant as, in the future, diarrhoea severity and C4 should be available for physicians before starting therapy.

The model fit will be assessed by inspection of scaled residual plots and QQ-plots.

**Sensitivity analyses:** The robustness of the statistical modelling of the primary endpoint will be addressed in sensitivity analyses of different approaches.

Different handling of missing values: 1) any missing diary day of the last seven treatment days and the patient treatment is set to failure; 2) excluding patients who drop out due to large pill size (the DB caps used for trial blinding are significantly larger than the colesevelam tablet), 3) using multiple imputations for missing values.

Strict Hjortswang's response criteria: no watery stools (Bristol stool type 6 or 7) during the last seven treatment days.

Different C4 cut-off used to define bile acid diarrhoea: C4 > 25 ng/mL; C4 > 58 ng/mL.

If possible, given that the study is not powered for stratification, we will assess remission rates in stratification intervals defined by C4 0–25 ng/mL, >25–46 ng/mL.

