## Power calculation

Based on the primary endpoint we assume

- a remission rate of 67% for colesevelam and 27% for placebo (36, 38).
- two-sided  $\alpha = 0.05$ , and  $\beta = 0.20$  (ie. 80% power); and 1:1 allocation.

Thus, we need 23 subjects with BAD in each arm (G.Power 3.1: z-test of two independent proportions).

As we include all patients with diarrhoea regardless of aetiology, the fraction or prevalence of BAD amongst these eligible patients is crucial. Of 71 subjects in our VABAD study, 59 patients had diarrhoea by Hjortswang criteria and deemed by  $C4 \geq 46$  ng/mL, 16 of the 59 had BAD (27%). In comparison with SeHCAT, Borghede et al. found that 41% of patients referred for SeHCAT had primary BAD defined with SeHCAT (44).

Thus to include 2 x 23 patients with BAD defined with  $C4 > 46$  ng/mL, we need

$$\frac{2 \times 23 \text{ BAD subjects}}{27\% \text{ BAD subjects among patients with diarrhoea}} = 170 \text{ patients with diarrhoea.}$$

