**Study Diary 2 – treatment period**

This diary registers the number of daily stools and consistency according to the Bristol stool form. The participants also note any AEs. The Study Diary 2 is commenced at Study Visit 2 and entails three periods

1. Study Visit 2 (Study day 8)
2. Run in period of five days (Study day 9 – 13)
3. Registration of Primary endpoint (Study day 14 – 20)

These periods are not separated in the diary. The diary also forms the subject's study participation card, with contact information to the relevant investigator or study nurse.

On study day 9, subjects set an "X" in the diary according to what treatment they think they are receiving: a) Colesevelam, b) Don't know, c) Placebo. This is used to assess initial blinding.

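### Prohibited anti-diarrhoeal or laxative use after randomisation has no stated analysis rule, so a diary made quiet by a barred drug can count as remission in the primary endpoint

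*Combined protocol and SAP*

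**What the plan says.** The Exclusion criteria list "Treatment with laxatives or anti-diarrhoeal drugs during the study", with one carve-out: "Except for stable dose the last four weeks of psyllium husk and opioids for pain". This is an eligibility item. The Withdrawal criteria cover only bilirubin and pregnancy.

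Under Primary endpoint, the plan adds one override to the diary result: "drop-outs are set as treatment failures in the ITT analysis if less than five of the last seven treatment days" are complete. With five or more complete days, "a mean of these days will be used for calculating the Hjortswang response criterium". The section on the Hjortswang criteria defines remission by stool frequency and watery stools alone: a mean below 3 stools and below 1 watery stool per day.

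On data capture, the section Study Diary 2 states: "This diary registers the number of daily stools and consistency according to the Bristol stool form". It adds adverse events and mentions no medication entry. The nurse calls on study days 10 and 14 are described as covering adverse events, compliance and dose. Visit 3 covers questionnaires, diary, adverse events and returned capsules. Anti-diarrhoeal medication is recorded at inclusion (Case Record Form) and anti-diarrhoeal medicine is asked about at the six-month follow-up.

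**The concern.** The protocol bars these drugs because they change the outcome being measured, yet the outcome rule takes no account of them. A patient whose study treatment is not working, who takes an anti-diarrhoeal and then records few stools, is scored the same as a patient who remitted on study treatment.

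Non-remitters have most reason to take such a drug, and the plan expects far more of them on placebo. The likely effect is therefore a higher placebo remission rate and a smaller difference. The primary population is small enough for one or two patients to matter. If use is not recorded during treatment, its effect cannot be examined afterwards. If it is noticed informally, the handling could be chosen once results are known.

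**Working it through.** **1. Could another part of the plan catch this case?** Take a patient with seven complete endpoint days, a barred anti-diarrhoeal taken during that week, and means below both thresholds.

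- Failure rule: not triggered, because the diary is complete.
- Hjortswang criterion: met, so the patient is a remitter.
- Sensitivity analyses under Primary endpoint: they vary missing data, strictness of response, C4 cut-off and modelling. None concerns other drugs. The strict criterion (no watery stools) changes the threshold, not the cause of the result.
- Per-protocol analyses (secondary endpoints 1 and 3): they impute missing data as if patients had adhered. This patient has no missing data.
- Expected missing data and drop-outs: deals with drop-out and missingness only.

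By contrast, under Study visit 2, alcohol and statin/fibrate violations do have a stated consequence.

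**2. The plan's own figure.** Inputs from Power calculation: "a remission rate of 67% for colesevelam and 27% for placebo", two-sided α 0.05, 80% power, 1:1 allocation, and "Thus, we need 23 subjects with BAD in each arm". For a pooled z-test with n per arm,

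power = Φ{ [d√n − 1.96√(2p̄(1−p̄))] / √(p₁(1−p₁) + p₂(1−p₂)) }.

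With d = 0.40, n = 23, p̄ = 0.47: (1.918 − 1.383) / 0.647 = 0.827, so power = 79.6%. Solving for 80% gives 23.2 per arm (24 when rounded up). The plan's 23 is reproduced to within rounding.

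**3. Effect on the difference.** Let u be the share of an arm's non-remitters who are converted, meaning that they take a barred drug, complete at least five days and therefore meet both thresholds. Planned non-remitters are 1 − 0.67 = 0.33 on colesevelam (c) and 1 − 0.27 = 0.73 on placebo (p).

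Observed difference = (0.67 + 0.33u_c) − (0.27 + 0.73u_p) = 0.40 + 0.33u_c − 0.73u_p.

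- Equal rates: 0.40 × (1 − u), smaller for any u above zero.
- The difference grows only if u_c/u_p exceeds 0.73/0.33 = 2.2.

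**4. Illustrations at 23 per arm.** Every rate of use here is an assumption.

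| Scenario | Colesevelam v placebo | Difference | Power |
|---|---|---|---|
| No conversion | 67.0% v 27.0% | 0.400 | 79.6% |
| One placebo patient (27% + 1/23), none on colesevelam | 67.0% v 31.3% | 0.357 | 68.8% |
| Same placebo rate (u = 0.0435/0.73 = 6.0%) in both arms | 69.0% v 31.3% | 0.376 | 73.8% |
| Two placebo patients (27% + 2/23), none on colesevelam | 67.0% v 35.7% | 0.313 | 56.9% |
| Same placebo rate (u = 11.9%) in both arms | 70.9% v 35.7% | 0.352 | 67.9% |
| u = 20% in both arms | 73.6% v 41.6% | 0.320 | 59.8% |
| u = 10% on colesevelam only | 70.3% v 27.0% | 0.433 | 86.1% |

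These are powers for the simple test used in the sample-size calculation. The planned mixed model with baseline adjustment will differ somewhat.

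**The case against.** The strongest reply is that scoring the observed diary, whatever else was taken, is a recognised treatment-policy approach. The plan describes its ITT analysis as an effectiveness estimand reflecting real-world effect. That choice would be defensible, but the plan does not state it for other medication. It would still require use to be recorded and a sensitivity analysis to be named.

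Several mitigating points also stand. Treatment lasts 12 days, patients judged at high risk of non-compliance are excluded, nurse calls support compliance, and lack of effect can be met by titration. Use may be rare. Partial suppression that leaves either mean above its threshold changes nothing. If one patient converts in each arm (each rate + 1/23), power is 79.5%, almost unchanged. The recording gap is inferred from silence, because the diary and case record forms are not reproduced and the overview chart is not readable.

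A reader might infer three stronger things that the documents do not support:

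- That only an incomplete diary makes a failure. Patients who miss the Hjortswang thresholds also fail. The point is that no event other than insufficient diary days overrides the diary.
- That the comparison is biased towards no effect. The documents give no rate of use, so bias is conditional and its direction is inferred.
- That the exclusion criterion would remove users from the analysis after randomisation. Nothing says so, and the section Subjects with diarrhoea defines the ITT population without such a removal.

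**Conclusion.** The gap is real: as written, the primary endpoint can count a drug-suppressed diary as remission, and no planned analysis would show it. The difference shrinks if non-remitters convert equally often in both arms, or more often on placebo. It would grow only if colesevelam non-remitters converted more than about 2.2 times as often.

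The size cannot be derived from the documents. One placebo conversion costs about 11 percentage points of power if use is on placebo only (79.6% to 68.8%) and about 6 if non-remitters in both arms convert equally often (79.6% to 73.8%). These figures assume the planned 67% and 27% and exactly 23 patients per arm. The point should be settled before unblinding, but it does not show that the trial's result would be wrong.

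**What to change.** 1. **Recording.** State that prohibited anti-diarrhoeal and laxative use during treatment is recorded at the nurse calls and at visit 3. The day-14 call falls at the start of the endpoint week (days 14–20), so visit 3 would carry most of this.
2. **Classification.** Add to Primary endpoint: in the ITT analysis, a randomised patient with recorded prohibited anti-diarrhoeal use in the seven endpoint days stays in the ITT set and is classified as not in remission.
3. **Sensitivity analysis.** Repeat the primary analysis with the diary scored as observed.
4. **Laxatives.** Report use by arm.

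The permitted stable psyllium and opioids are unaffected. This concerns outcome classification only, not patient care.

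The cost is a few sentences of analysis-plan wording and one added question at existing contacts. The downside is that a few patients move to failure, including some with only isolated use who might have been in remission anyway, and that classification rests partly on recall. The as-observed analysis shows how much the rule matters.
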